Tuberculin PPD – This drug is used as part of a tuberculin PPD test as performed by injecting .1mL of purified tuberculin PPD subcutaneously in the skin. This is the standard dosing for a test to determine if a patient is infected with *Mycobacterium tuberculosis*.

Lidocaine/epinephrine – 3 mL injection at the biopsy site. Lidocaine-HCL 1% w/ epinephrine (1:100,000)

- b. Justification and safety information if FDA approved drugs will be administered for non-FDA approved indications or if doses or routes of administration or participant populations are changed.

N/A

- c. Justification and safety information if non-FDA approved drugs without an IND will be administered.

N/A An IND has been given approval to proceed.

7. Study Statistics

- a. Primary outcome variable.
Percent PP-NRS reduction between baseline and week 12.
- b. Secondary outcome variables.

Analysis of PN-IGA, PROMIS Itch Questionnaire, PAS, 5D Pruritus Score, DLQI, HADS, and EQ-5D and detect differences between baseline through Week 12. An ordinal regression will be used because these are non-parametric, ordinal scales.

Approval Date: 3/16/2022
Principal Investigator: [name]
Application Number: IRB00262268

c. Statistical plan including sample size justification and interim data analysis.

The trial arms of PN and CPUO will be used to conduct subsequent analyses of treatment efficacy. We will treat a p-value of <0.05 as statistically significant, and all tests will be two-tailed. For the primary endpoint, ANOVA will be used to analyze differences in percent PP-NRS reduction (baseline and week 12) with the inclusion of other covariates. We will use a Least-Square means to account for missing data or unbalanced design. We will conduct a two-way analysis of the response variable (PP-NRS percent reduction) by classification variables: specifically, whether the patient has PN or CPUO, and week of treatment. We can derive all LS-means differences from every permutation of week or diagnosis, relative to Week 0 (baseline, prior to treatment). We will incorporate a 95% confidence limit for a significant difference in LS-mean difference between the control group and other groups.

Unlike the primary efficacy endpoint, the secondary endpoints do not have explicit, clinically meaningful changes outlined in the literature. As such, we will look for significant downregulation in itch assessments, and significant improvements in quality of life and sleep measures.

Secondary aims will be analyzed using appropriate statistical tests as outlined below, and missing data will be corrected with Multiple Imputation (MI) and we will assume that missing data is Missing at Random (MAR).

For secondary analyses, a multivariable logistic regression will be used to calculate the odds ratios of different study arms (PN and CPUO) achieving a 4-point reduction in PP-NRS and in SD NRS.

To analyze the PN-IGA, PROMIS Itch Questionnaire, PAS, 5D Pruritus Score, DLQI, HADS, and EQ-5D and detect differences between baseline through Week 12, an ordinal regression will be used because these are non-parametric, ordinal scales.

IgA for PN is not validated in the US, so we are using it as an additional secondary efficacy measure. Appendix D has a simplified version we are applying to this study. Eczema and psoriasis IgA are similarly qualitative. Analysis of PN/CPUO IgA will be an ordinal scale based on qualitative scaling determined at the site visit. We will analyze IgA with an ordinal regression, same as other scales mentioned above.

Atopy will be defined as a binary variable where patients have 2 out of 3: underlying history of atopic dermatitis, history of seasonal allergies, or asthma.

Among PN patients taking 200 mg of abrocitinib, we will use a linear regression to compare PP-NRS reduction from baseline with week 12, among PN patients with atopy and PN patients without atopy.

Approval Date: 3/16/2022
Principal Investigator: [name]
Application Number: IRB00262268

d. Early stopping rules.

Patients may withdraw at any time or they will be asked to end participation if the physician determines that discontinuation is in the patient's best interest. Data collected may be used if any endpoints are reached.

8. Risks

a. Medical risks, listing all procedures, their major and minor risks and expected frequency.

Foreseeable and known risks of study drug

There is a risk that participants might experience discomfort or side effects with the use of the study drug or procedures. Some of them are still unknown at this stage. In some cases, **side effects can be serious, long-lasting, permanent, or life-threatening**. The study doctor is trained to take the appropriate measures to reduce risks and limit any discomforts you may experience.

Side Effects:

- The most commonly reported side effects are:
 - Nausea (1 in 7 people)
 - Nasopharyngitis (1 in 8 people)
 - Headache (1 in 25 people)
- Rare but serious side effects include:
 - Serious infection (less than 1 in 100 people)
 - Vomiting (1 in 85 people)
 - Decreased platelet counts (1 in 75 people)
-

Skin Biopsy

- Small risk of bleeding
- A scar may form, but is likely to fade over time
- All procedures have a small risk of infection

Blood Draw

Taking blood may cause discomfort, bleeding, or bruising where the needle enters the body. In rare cases, it may result in fainting. There is a small risk of infection.

Interviews or questionnaires

Participants may get tired or bored when we are asking you questions or they are completing questionnaires. Participants do not have to answer any question they do not want to answer.

Identifiable private information

There is the risk that information about participants may become known to people outside this study.

Approval Date: 3/16/2022
Principal Investigator: [name]
Application Number: IRB00262268

b. Steps taken to minimize the risks.

Participants will be screened for conditions that may increase risk of study drug or skin biopsy.

All participant data will be deidentified and stored on a secure server in order to protect privacy to the utmost degree.

c. Plan for reporting unanticipated problems or study deviations.

All unanticipated problems and study deviations will be reported to the primary investigator, [name], as well as the IRB immediately upon discovery.

d. Legal risks such as the risks that would be associated with breach of confidentiality.

As this study involves personal health information, there is a risk of breach of confidentiality. Additionally, as there are genetic studies planned as part of this study, there is a risk that this information could be disclosed with a breach of confidentiality.

e. Financial risks to the participants.

There is a small financial risk to participants if they suffer from severe side effects that impact their day-to-day life and require additional medical care or potentially missing work. These are not anticipated to be significant risks for this study.

9. Benefits

a. Description of the probable benefits for the participant and for society.

There is potential benefit to the participant if abrocitinib shows efficacy in improvement for conditions of chronic itch. There is also benefit for society of contributing to the understanding of these chronic itch conditions for which no approved therapies currently exist.

10. Payment and Remuneration

Approval Date: 3/16/2022
Principal Investigator: [name]
Application Number: IRB00262268

a. Detail compensation for participants including possible total compensation, proposed bonus, and any proposed reductions or penalties for not completing the protocol.

Participants will receive up to \$400 for successful completion of the study. They will receive \$50 for completion of study visits 1, 3, 4, 5, and 7 and \$75 for completion of study visits 2 and 6. Participants will receive a check at the end of the study visit or a check will be mailed to their home address.

Participants will also receive reimbursement for parking costs.

11. Costs

a. Detail costs of study procedure(s) or drug (s) or substance(s) to participants and identify who will pay for them.

There are no costs to participate in the study.

12. Transfer of Materials

Transfer of biospecimens from Johns Hopkins to another organization for research purposes and receipt of biospecimens from an outside organization for your research must adhere to JHU policies for material transfer (<https://ventures.jhu.edu/faculty-inventors/forms-policies/>) and biospecimen transfer (https://hpo.johnshopkins.edu/enterprise/policies/176/39187/policy_39187.pdf?_=0.622324232879).

Please complete this section if your research involves transfer or receipt of biospecimens.

a. Will you **receive** biospecimens from an external entity for this research? [Yes/No].
If “Yes”, please confirm you will secure an MTA/research agreement from the appropriate office (JHTV/ORA) prior to transfer.
See: <https://ventures.jhu.edu/technology-transfer/material-transfer-agreements/>.

b. Will you **transfer** biospecimens to an external entity as part of this research? [Yes/No]
If “Yes”, please address each of the following:
1) Describe the nature of the research collaboration with the external entity and the rationale for the transfer. (Include an explanation of your intellectual contribution to the design of the research study, resulting data and sharing, and participation in the planned publications.)
2) Please confirm you will secure an MTA through the appropriate office (JHTV or ORA) prior to transfer.
(See: <https://ventures.jhu.edu/technology-transfer/material-transfer-agreements/>.)
Already obtained: please see page 23, section 4.

Approval Date: 3/16/2022
Principal Investigator: [name]
Application Number: IRB00262268

3) If the biospecimens you intend to transfer were obtained through clinical or research procedures at Johns Hopkins and “Other” is selected in Item 4, Section 23, please submit the following items in that Section:

- a. A pdf version of a completed JHTV Online “Material Transfer Agreement Request Form for Outbound Material” <https://ventures.jhu.edu/technology-transfer/material-transfer-agreements/> OR a copy of the COEUS PD (Proposal Development Summary).
Already obtained: please see page 23, section 4
- b. A completed Biospecimen Transfer Information Sheet
https://www.hopkinsmedicine.org/institutional_review_board/forms/.
Already obtained: please see page 23, section 4
- c. A signed and dated “De-identified Human Subject Certification”
https://www.hopkinsmedicine.org/institutional_review_board/forms/
Already obtained: please see page 23, section 4
- d. Approval documents from recipient site, if applicable.
N/A
- e. Copies of the consent forms associated with the IRB protocols under which the biospecimens were collected, with language appropriate to this transfer highlighted.
Already obtained: please see page 23, section 4
- f. The name of the specialist you are working with in ORA to complete a contract/MTA.
Already obtained: please see page 23, section 4
[name]

Please see the following website for more information about transferring human biospecimens to outside entities:
https://www.hopkinsmedicine.org/institutional_review_board/news/announcement_transfer_human_biospecimens_outside_entities.html.

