 - HIV screening test. You may be asked to sign a separate State of Maryland consent form for this HIV test. If the HIV test is positive it does not always mean you are infected with the HIV virus. It does mean you will need further testing and you will receive counseling about this. The law requires us to report positive tests to the health department. This reporting will include information that identifies you (for example name, date of birth, home address, phone number, etc.) as required by Maryland law. The health department may use this information to contact you for further follow up and/or to help conduct health surveillance activities aimed at preventing or controlling diseases.
 - Only for participants with known history of HIV: CD4+ T cell count and viral load will be evaluated at screening and

at the end of the study drug period. This will be approximately 10 mL (less than one tablespoon) blood in addition to total amount of blood.

- Pregnancy testing: only for women capable of having children: by blood test at the first study visit and urine sampling test every 4 weeks at site visit.
- **For Study Visits 2 through 7 (Week 0 – 16) the following procedures will be done according to the schedule above: Visits will be conducted within the specified week or within +/- 5 days of the intended week.**
 - Dispensing of Investigational Drug: All participants will receive abrocitinib beginning at visit 2. This will be taken as a daily oral dose of 200mg in tablet form. This therapy will continue for 12 weeks (through visit 6).
 - Electronic diary: Participants will be asked to complete a diary daily in the morning. This will include questionnaires to evaluate the severity of symptoms such as itch and pain and asking participants to rate their quality of sleep during the last night. The completion of the diary will take approximately 10 minutes. The study doctor or site staff will train participants on how to use the diary during Visit 1 and give you instructions on how to complete these assessments. This diary must be returned to the site at the end of study visit.

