 - Questionnaires: Participants will need to complete up to 6 questionnaires on a tablet. This will provide insight into how their disease is affecting their quality of life and to provide information on symptoms and the impact of the disease on quality of life. Total duration of completion of these questionnaires will take approximately 30 minutes. Also, the study doctor will need to evaluate the severity of symptoms and complete up to 2 questionnaires at each visit. These questionnaires include:
 - PP-NRS
 - DLQI
 - PROMIS PIQ T Score
 - 5D Pruritis Score
 - SD-NRS
 - EQ-5D
 - HADS
 - PAS
 - PN-IGA
 - Physical examination: Examination of major body organs.
 - Vital sign: Measurement of blood pressure, heart rate, respiratory rate, body temperature, and weight.
 - Photographs: Digital photographs of the pruritic areas will be taken at each study visit. These photographs will avoid any identifying areas/marks including the face, tattoos or identifying birth marks.
 - Skin biopsy: A 4mm punch biopsy of the affected pruritic area will be taken at visit 2 and visit 6. This will involve injection of lidocaine and epinephrine followed by taking the biopsy. Participants will not feel pain, only pressure. A stitch will be placed and care instructions will be given. Participants will return for suture removal 7 to 10 days after the biopsy.

Approval Date: 3/16/2022
 Principal Investigator: [name]
 Application Number: IRB00262268

- Blood collection at all visits. The total amount of blood to be taken in this study for each participant is approximately 130mL (approximately 9 tablespoons). These samples will be used to test:
 - Hematology (blood count), biochemistry, Biomarker testing

Examination	Visit 1 Screening Week (-4)	Visit 2 (Week 0)	Visit 3 (Week 2)	Visit 4 (Week 4)	Visit 5 (Week 8)	Visit 6 (Week 12)	Visit 7 (Week 16)
Informed Consent	X						
I/E criteria – Full list above, but tests include: TSH, Hepatitis panel, HIV antibodies, CD4 count, CBC, CMP, lipid panel, PPD test, hCP test for pregnancy among WOCBP. Blood draw criteria is below.	X	X					
Demographics & Medical History	X						
Vital signs	X	X	X	X	X	X	X
Skin examination	X	X	X	X	X	X	X
PP-NRS		X	X	X	X	X	X
DLQI		X	X	X	X	X	X
PROMIS PIQ T-Score		X	X	X	X	X	X
5D Pruritus Score		X	X	X	X	X	X
SD-NRS		X	X	X	X	X	X
EQ-5D		X	X	X	X	X	X
HADS		X	X	X	X	X	X
PAS		X	X	X	X	X	X
PN-IGA		X	X	X	X	X	X
Photographs*		X	X	X	X	X	X
Dispense abrocitinib		X	X	X	X		
Adverse Event Monitoring		X	X	X	X	X	X

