Itch Diary Review/compliance			X	X	X	X	X
Skin biopsy		X				X	
Plasma/PBMC isolation from blood draw		X				X	X
Labs from Blood Draw (CMP, CBC, Lipid panel, IgE)	X	X	X	X	X	X	
Patient who are HBcAB-positive and HBV DNA-negative at baseline require HBV DNA monitoring		X	X			X	

Approval Date: 3/16/2022
Principal Investigator: [name]
Application Number: IRB00262268

b. If your study involves data/biospecimens from participants enrolled under other research studies with a written consent or under a waiver of consent, please list the IRB application numbers for those studies. Please note: Certificate of Confidentiality (CoC) protections applied to the data in source studies funded by NIH or CDC will extend to this new study if the funding was active in 2016. If this situation applies, Section 36, question 6 in the application will need to be answered "Yes" and "Hopkins Faculty" should be selected in question 7. No other documents are required.

N/A

c. Study duration and number of study visits required of research participants.

Participants will be in this trial for up to 20 weeks including screening and follow-up.

d. Blinding, including justification for blinding or not blinding the trial, if applicable.

This study will not be blinded. All participants will receive study drug therefore blinding is not applicable.

e. Justification of why participants will not receive routine care or will have current therapy stopped.

Participants will need to stop current therapy in order to qualify for the study. In order to clearly elucidate the efficacy of abrocitinib against PN and CPUO, it is important for concurrent therapies to be halted. It is also important to note that the majority of therapies offered to these patients have poor efficacy in controlling PN and CPUO.

Participants will continue to receive other routine care.

f. Justification for inclusion of a placebo or non-treatment group.

There is no placebo group in this study. As this is an early phase, small study, we will not include a placebo group. If the data is suggestive of efficacy, a full blinded, and placebo-controlled study will be done.

g. Definition of treatment failure or participant removal criteria.

Approval Date: 3/16/2022
Principal Investigator: [name]
Application Number: IRB00262268

Discontinuation Criteria

Discontinuation from Study Treatment

Temporary Interruption of Investigational Product

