PBMCs will be isolated from patient whole blood at the same time points above, at Week 0, at Week 12, and at Week 16. To analyze multiple immune cell populations, we will use the Maxpar Direct Immune Profiling Assay from Fluidigm, which uses Cytometry by time-of-flight (CyTOF), a novel variant of conventional flow cytometry. This kit supplies 30 metal-tagged antibodies as a dry pellet, with additional channels/metal tags allowing for additional targets. 37 immune cell populations can be characterized from PBMCs, and CyTOF technology will allow for complete protein quantification of all selected markers.

These tests will not be performed at a CLIA certified laboratory because these are not clinical grade tests and are designed only for research purposes. No results from these tests will be shared with participants as these are not intended for diagnostic purposes.

5. Inclusion/Exclusion Criteria

Inclusion Criteria:

- Males or female participants between ages 18-80 years at time of signing informed consent
- A clinical diagnosis of prurigo nodularis, defined by the presence of at least 10 pruritic nodules on at least 2 different anatomic locations (with each arm, leg, and anterior and posterior trunk considered distinct anatomic locations)
OR
- Subject has ongoing chronic pruritus of unknown origin, which must be present on multiple segments on the body. CPUO patients must not have known dermatologic or systemic conditions, that in the opinion of the investigator, are the cause of patient's pruritus
- Subject has moderate to severe pruritus, defined as average worst itch numeric rating scale – PP-NRS ≥ 7 (range 0-10, higher score indicating greater degree of pruritus severity) in the 7 days prior to the Screening Visit.
- Must read and understand the informed consent approved by the institutional review board (IRB) governing the site and provide written informed consent.

Sex

Approval Date: 3/16/2022
Principal Investigator: [name]
Application Number: IRB00262268

a) Female participants are eligible for the study if they are not pregnant, planning to become pregnant or breastfeeding during the study and one of the following applies:

- Female participant is not a WOCBP: Female patients of non-child-bearing potential are not required to use birth control and they are defined as:
 - Women who are infertile due to surgical sterilization (hysterectomy, bilateral oophorectomy, or tubal ligation)
 - Post-menopausal – defined either as

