 - A woman at least 50 years of age with an intact uterus, not on hormone therapy, who has either
 - Cessation of menses for at least 1 year
 - At least 6 months of spontaneous menstruation with follicle-stimulating hormone >40 mIU/mL
 - Women aged 55 years or older who are not on hormone therapy, and who have had at least 6 months of spontaneous amenorrhea
 - Women aged 55 years or older who have a diagnosis of menopause

OR

- If female participant is a WOCBP:
 - a. Female patients of child-bearing potential who are abstinent (if this is complete abstinence, as their preferred and usual lifestyle) or in a same-sex relationship (as part of their preferred and usual lifestyle) must agree to either remain abstinent or stay in a same-sex relationship without sexual relationships with the opposite sex.
 - b. Total abstinence is defined as refraining from intercourse during the entirety of the study and for at least 1 week following the last dose of investigational product. Periodic abstinence such as calendar, ovulation, symptothermal, post-ovulation methods and withdrawal are not acceptable methods of contraception.
 - c. Otherwise, female patients of childbearing potential must agree to use 2 effective methods of contraception, where at least 1 form is highly effective, for the entirety of the study and for at least 1 week following the last dose of investigational product.
 - d. The following contraception methods are considered acceptable (the patient should choose 2, and 1 must be highly effective [defined as less than 1% failure rate per year when used consistently and correctly]):
 - Highly effective birth control methods:
 - Combined (estrogen and progestogen containing) hormonal contraception associated with inhibition of ovulation: oral, intravaginal, or transdermal
 - Progestogen- only containing hormonal contraception associated with inhibition of ovulation: oral, intravaginal, or transdermal
 - intrauterine device (IUD)/intrauterine hormone-releasing system (IUS)
 - vasectomized male (with appropriate post-vasectomy documentation of the absence of sperm in the ejaculate).
 - Effective birth control methods:
 - Male or female condom with spermicide. It should be noted that the use of male and female condoms as a double barrier method is not considered acceptable due to the high failure rate when these methods are combined.

Approval Date: 3/16/2022
Principal Investigator: [name]
Application Number: IRB00262268

- Diaphragm with spermicide

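### One option in the post-menopausal definition says menstruation where amenorrhea must be meant, so a still-menstruating woman aged 50 or over with FSH >40 mIU/mL is exempt from contraception and may miss pregnancy tests

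*Combined protocol and SAP*

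**What the plan says.** In Section 5, under Sex, item a), women are divided into those of child-bearing potential (WOCBP) and those who are not. The contraception exemption for the second group is explicit: "Female patients of non-child-bearing potential are not required to use birth control". The group consists of surgically sterilized women and post-menopausal women.

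One post-menopausal route opens with "A woman at least 50 years of age with an intact uterus, not on hormone therapy, who has either" and then gives two alternatives. The first is that periods stopped at least a year ago. The second is "At least 6 months of spontaneous menstruation with follicle-stimulating hormone >40 mIU/mL". A separate route for older women reads "Women aged 55 years or older who are not on hormone therapy, and who have had at least 6 months of spontaneous amenorrhea". A further route covers women of 55 or over with a diagnosis of menopause.

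Pregnancy testing is described in two places. The Screening Visit text in Section 4a offers it "only for women capable of having children: by blood test at the first study visit and urine sampling test every 4 weeks". The eligibility row of the visit schedule lists an "hCP test for pregnancy among WOCBP".

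**The concern.** A definition of post-menopausal that a woman satisfies by menstruating contradicts itself. The text is operative: meeting any one of the listed routes removes the contraception duty. A WOCBP must either keep to abstinence or a same-sex relationship as her usual lifestyle, or use two methods of contraception with at least one highly effective. A woman classed as non-WOCBP has no such duty.

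What is at stake is participant protection. The plan itself treats pregnancy as serious: it bars entry in Section 5 and requires the drug to be stopped under Permanent Discontinuation. A woman who can still conceive could take 200 mg of abrocitinib daily for 12 weeks with no contraception requirement and possibly without the tests that would reveal a pregnancy.

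**Working it through.** The plan gives no figure to reproduce here. The check is to read the definition against its neighbours and against the rules that depend on it.

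**Is the word wrong?** The document settles this without any outside source.

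- The option sits under a post-menopausal heading.
- Its sibling requires that periods have stopped.
- The age-55 route uses the same 6-month construction with amenorrhea.
- The note on local guidelines at the end of the contraception list concerns methods of birth control, not who counts as WOCBP.
- Replacing one whole clinical word by its opposite is not a plausible text-extraction fault.

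**Who is classified differently?** Take women with an intact uterus, not on hormone therapy, not surgically sterilized, and with no other exempting route:

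| Woman | As written | With amenorrhea |
|---|---|---|
| 50 or over, menstruating for 6 months or more, FSH >40 mIU/mL | not WOCBP | WOCBP |
| 50 to 54, amenorrhea for 6 months but under 1 year, FSH >40 mIU/mL | WOCBP | not WOCBP |
| 50 or over, no periods for 1 year or more | not WOCBP | not WOCBP |
| 55 or over, amenorrhea for 6 months or more | not WOCBP | not WOCBP |

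The first row is the safety problem. The second is the reverse error: women whom the option evidently meant to exempt stay under the contraception rule, which is a burden but not a harm. It stops at 54 because the age-55 route requires only 6 months of amenorrhea and no FSH result.

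**For how long?** The visits are at weeks -4, 0, 2, 4, 8, 12 and 16. The span is 16 - (-4) = 20 weeks, which agrees with Section 4c: "Participants will be in this trial for up to 20 weeks including screening and follow-up". Treatment runs from week 0 to week 12, so 12 of those weeks are on drug.

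**Which pregnancy tests could be lost?** This assumes that all testing follows WOCBP status.

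- Blood: 1 test, at the first visit.
- Urine, every 4 weeks at a site visit: weeks 0, 4, 8, 12 and 16 = 5 tests, or weeks 4, 8, 12 and 16 = 4 if counted from first dose.
- Total: 1 + 4 = 5 to 1 + 5 = 6 tests.
- Of these, 3 (weeks 4, 8 and 12) fall after first dose and up to the end of treatment.

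**The case against.** The strongest reply accepts the error and disputes its reach.

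- **The slip is obvious.** An investigator would have to call a woman with regular periods post-menopausal, against the heading and both neighbouring options. That makes harm less likely. But eligibility criteria are applied and audited as written. A site that silently reads amenorrhea departs from the approved text, and a site that follows the text exempts the wrong woman.
- **FSH is not among the listed study tests.** Neither the screening bloods in Section 4a nor the schedule names it, so this route works only if the site adds the test or already holds a result. This is correct and narrows the reach. It does not close the route, and the schedule's list is not worded as exhaustive.
- **The testing consequence is inferred.** The Section 4a wording rests on capability of having children, and a menstruating, unsterilized woman fits it. The WOCBP wording is in the eligibility row, marked only for Visits 1 and 2, and does not plainly govern the later urine tests. This stands. It is why the claim is only that she may miss tests, and why the counts are conditional.
- **Other safeguards remain.** Every woman must be neither pregnant nor planning pregnancy, pregnancy stops the drug, and the investigator may exclude anyone at unacceptable risk. These reduce the risk, but none restores the contraception duty, and stopping the drug depends on the pregnancy being detected.

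**Conclusion.** The concern holds. The word is wrong as written, in a rule that decides who must use contraception, and no other text corrects it. The loss of the contraception duty follows directly from the wording and could last for a study of up to 20 weeks, 12 of them on drug. The possible loss of 5 to 6 pregnancy tests per woman rests on two assumptions: that testing follows WOCBP status, and that the 4-weekly urine tests fall at the visits counted above.

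The criterion formally covers ages 50 to 80, the upper limit being the trial's own, but those affected are likely to be near the lower end. The documents do not say how many such women would enrol; the number is probably small. No endpoint, analysis or sample size is touched. The correction is worth making because it protects participants at almost no cost.

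**What to change.** By amendment, replace the word menstruation with amenorrhea in this option, so that it requires at least 6 months of spontaneous amenorrhea together with FSH above 40 mIU/mL. Until the amendment is approved, instruct the site in writing to treat any still-menstruating woman without surgical sterilization as WOCBP, for both contraception and pregnancy testing.

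The cost is one word in an amendment and a short note to the site. No visit, procedure or analysis needs to change.
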